Project title: A Comparison of the Post-Cesarean Section Analgesic Effects of Neuraxial Duramorph vs. Bilateral Transversus Abdominal Plane (TAP) Block With Combined Bupivacaine and Liposomal Bupivacaine (Exparel).

Clinicaltrials.gov name

A Comparison of the Post-C/S Analgesic Effects of Neuraxial Duramorph vs Bilateral TAP Block With Liposomal Bupivacaine

Submitted to IRB 4-5-2018

IRB# 2018-4-1-MMC

NCT: 03638011

Summary/Program Objective:

The primary objective is to reduce or eliminate the use of all narcotics/opiates for post Cesarean section pain management. We hypothesize that in comparison with epidural or intrathecal Duramorph, a TAP block with liposomal bupivacaine (Exparel) will provide better, longer-acting pain control and will significantly reduce the use of post-operative IV or p.o. opiates. This is a prospective, randomized clinical trial. We will compare the analgesic efficacy and duration of an ultrasound guided bilateral TAP Block (with combined bupivacaine and liposomal bupivacaine) to Duramorph (an opiate). Neuraxial duramorph provides approximately 24 hours of pain relief (analgesia), whereas a bilateral TAP block with liposomal bupivacaine is expected to provide up to 72 hours of analgesia. The patient's analgesia will be assessed by reviewing patient-reported pain intensity based on an 11-point numeric rating scale (NRS; 0= no pain, 10= worst possible pain) and post-operative opiate usage. Secondary objectives include a comparison of the opiate related post-surgical adverse events (AEs) (defined as somnolence, sedation, confusion, respiratory depression, dry mouth, nausea, vomiting, constipation, urinary retention and pruritus), and overall satisfaction with their postsurgical analgesia (patient-reported, using an 11 point scale whereby 0= not at all satisfied and 10= extremely satisfied) at hospital discharge.

Purpose of the study:

To determine if a bilateral transversus abdominal plane block with combined bupivacaine and liposomal bupivacaine can provide safe, effective, long-acting pain control that minimizes narcotic usage.

1. Specific Aims:

All patients will have neuraxial anesthesia (either a spinal or epidural) for their non-urgent or elective Cesarean section.

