The control group (Group 1) will receive either intrathecal or epidural Duramorph (preservative-free morphine sulfate). Post-operatively, participants will have orders to receive, on an as-needed basis, IV/oral acetaminophen and/or IV/oral non-steroidal anti-inflammatory drugs (NSAIDS) for mild-moderate pain, and narcotics for severe pain; specifically- oxycodone or hydromorphone. All patients must receive acetaminophen and NSAIDS (unless contraindicated) before receiving narcotics. This multi-modal pain management regimen is our current standard of care.

The experimental group (Group 2) will also receive a spinal or epidural anesthetic. This group will not receive neuraxial Duramorph for post-operative pain. Instead, the patient will receive an ultrasound guided bilateral TAP block with a combination of bupivacaine and liposomal bupivacaine solution immediately after the Cesarean section. Additionally, they will receive the same post-operative analgesia orders as group 1.

Specific Aim 1) To show that participants in the TAP block group will have better and longer acting pain relief than the Duramorph group. We will record and compare patient-reported post-operative pain intensity using an analogue visual score card with an 11-point numeric rating scale at 6, 24,48 and 72 hours.

Specific Aim 2) To show that the TAP block group will use less post-operative narcotics than the Duramorph group. We will measure and analyze the times at which participants in both groups request narcotics and the amount administered. We will also record each participant's pain level prior to receiving narcotics. It is anticipated that participants in TAP Block group will need significantly less post-operative narcotics when compared to the Duramorph group (standard of care)

Specific Aim 3) The TAP block group will have a decreased incidence of opiate- related side effects such as somnolence, sedation, confusion, respiratory depression, dry mouth, nausea, vomiting, constipation, urinary retention, and pruritus (itching).

Specific Aim 4) To measure patients' overall satisfaction with their postsurgical analgesia. Using an 11 point scale where 0= not at all satisfied and 10= extremely satisfied, we will record their overall satisfaction with their postsurgical analgesia. It is anticipated that participants in the TAP block group would report their pain control as being better than participants in the Duramorph group.

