This is a prospective, randomized study evaluating the effectiveness of abdominal analgesia when using 266 mg EXPAREL delivered into the bilateral TAP blocks. TAP blocks are an excellent method for providing adequate analgesia following lower abdominal surgery (3-6). To be eligible for the study, the patient has to be undergoing a non-urgent Cesarean section (either elective, or for non-urgent conditions such as failure to progress) with neuraxial anesthesia via an epidural, spinal or combination epidural/spinal. When patients arrive for their Cesarean section they will be assessed if they are eligible for the study and they will be asked to participate in the study after the risks and benefits are explained. If a patient does not want to participate, they will be offered TAP blocks with regular bupivacaine. Those patients who wish to participate will be asked to sign a study consent form. Patients that decide to participate in this study will be randomized to either group 1 or group 2 (like the

flip of a coin). Both groups will receive standard neuraxial anesthesia for their Cesarean Section and post-operative standard of care breakthrough medications for post-operative pain control. They will be randomized to receive either (group 1) standard neuraxial anesthesia with neuraxial Duramorph for post-operative pain or (group 2) standard neuraxial anesthesia without neuraxial Duramorph and a transversus abdominal plane (TAP) blocks immediately after surgery, with a mixture of bupivacaine and Exparel, for post-operative analgesia.

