There are only two groups in this study: Group 1 will have our present standard of care: neuraxial anesthesia, with Duramorph added to the epidural or spinal for post-operative pain. Group 2 will also have neuraxial anesthesia but will receive bilateral TAP blocks for post-operative pain control with 40 ml of 0.25% regular standard bupivacaine and with 20 ml of liposomal bupivacaine (Exparel) and 10-20 ml of normal saline (a salt solution, for a total of 70-80mls: 35-40 ml on each side). The TAP block plane will be identified with ultrasound. A 100 mm needle will be ultrasound guided into the TAP plane. 5-10 milliliters of normal saline will be used to hydro-dissect the plane. After hydro dissection 15 ml of 0.25% regular standard bupivacaine will be injected followed by 10 milliliters of liposomal bupivacaine (Exparel) diluted with 5 ml of 0.25% regular standard bupivacaine. This will be repeated on the opposite side. We will follow pain levels closely after the Cesarean section. If patients request medication for breakthrough pain, they will be given Tylenol, first. If the pain persists, they will be given Toradol 30 mgs, unless contraindicated. For persistent pain, they may receive another dose of 30 mgs of Toradol, but for severe pain they will be offered oxycodone 5-10 mg, depending on the intensity of the pain. Patients must be given both Tylenol and Toradol, unless contraindicated, before receiving narcotics for severe pain. We will ask you a set of questions to assess to quality of analgesia (pain control): 1) How is your pain at that time point? 2) What was your highest pain score? And 3) Did you require narcotic pain medication, when did you receive it and what was your pain level at that time? To assist your evaluation of your pain, we will show you a card that has a visual analogue (Faces) pains scale combined with numerical (0-10) analogue scale (0 is no pain, 10 is the worst pain you can imagine). We will be recording your pain at

- 6 hours after the end of anesthesia or the TAP block
- 24 hours after the end of anesthesia or the TAP block.
- 48 hours after the end of anesthesia or the TAP block.
- And at 72 hours after the end of anesthesia or the TAP block.
- Before you leave the hospital, we will ask you to rate your pain control.

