At all-time points patients and/or nurses taking care of the patient will be asked about: somnolence (sedation or excessive tiredness), respiratory depression, hypoxia, dry mouth, nausea, vomiting, itching, constipation, urinary retention, sedation, and confusion.

We will also record time and date of any and all post-operative narcotics used by the patient as well as their pain scores just prior to receiving narcotics.

Additionally, patients will be asked about their overall satisfaction with postsurgical analgesia at the end of their hospital stay. If after Day 10±5, the investigator is made aware of an AE that occurred during this period of time, this will be reported to the IRB.

Eligibility Criteria:

Inclusion Criteria:

- Females, aged 18-45 years inclusive and ASA physical status 1-3.
- Undergoing non-urgent Cesarean section with neuraxial anesthesia/analgesia.
- Subjects must be physically and mentally able to participate in the study and complete all study assessments.
- Subjects must be able to give fully informed consent to participate in this study after demonstrating a good understanding of the risks and benefits of the proposed components of the TAP infiltration.

Exclusion Criteria:

- History of hypersensitivity or idiosyncratic reactions to amide-type local anesthetics
- Any subject whose anatomy, or surgical procedure, in the opinion of the Investigator, might preclude the potential successful performance of a bilateral TAP infiltration.
- Any subject who in the opinion of the Investigator, might be harmed or be a poor candidate for participation in the study.
- Any subject, who in the opinion of the Investigator, is on chronic pain medicine, including large doses of NSAIDs.
- Subjects who have received any investigational drug within 30 days prior to study drug administration, or planned administration of another investigational product or procedure during their participation in this study.

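### Aim 3 compares the incidence of opiate-related side effects, but symptoms are first asked about 6 hours after treatment, so persisting earlier symptoms cannot be told from new ones and pull the risk ratio toward 1.

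*Combined protocol and SAP*

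**What the plan says.** Specific Aim 3 (section 1) states: "The TAP block group will have a decreased incidence of opiate- related side effects". The Summary/Program Objective makes this a secondary objective and describes it as follows: "comparison of the opiate related post-surgical adverse events (AEs) (defined as somnolence, sedation, confusion, respiratory depression, dry mouth, nausea, vomiting, constipation, urinary retention and pruritus". An event is thus identified by its name on a list. Neither place requires the symptom to be new or worse, and no step assesses cause.

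Section 3, Research Design and Methods, says when the list is asked: "At all-time points patients and/or nurses taking care of the patient will be asked about". The first listed time is "6 hours after the end of anesthesia or the TAP block" and the last timed one is "And at 72 hours after the end of anesthesia or the TAP block", with 24 and 48 hours between. Specific Aim 1 has the same schedule for pain: "11-point numeric rating scale at 6, 24,48 and 72 hours". The remaining item, a rating of pain control before discharge, is also post-operative.

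The contact before surgery described in section 3 consists of the eligibility check, consent and randomisation. Eligible operations are elective ones or those "for non-urgent conditions such as failure to progress". The exclusion criteria do not name women who already have a listed symptom.

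**The concern.** Incidence means events that arise after treatment. A list asked only after treatment gives the presence of symptoms at those times. The two agree only if women are free of the symptoms beforehand, or if earlier symptoms are recorded and set aside. The plan provides for neither.

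Prior symptoms are plausible here. Women operated on for failure to progress come from labour, and section 3 explains somnolence broadly enough to include undue tiredness. Tiredness, nausea, dry mouth, itching or constipation could precede the neuraxial injection and still be reported at 6 hours.

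Such symptoms owe nothing to Duramorph or to rescue opioid. If they are counted, they add the same background to both arms, overstate both rates and make a real reduction harder to see. A pre-operative answer that was never collected cannot be reliably recovered afterwards.

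**Working it through.** **Inputs.** The documents give no side-effect rates, no pre-operative symptom prevalence, and no sample size, significance level or power for Aim 3. There is no design figure to reproduce. Everything below is assumed:
- true new-symptom rates p1 = 40% (Duramorph) and p2 = 20% (TAP);
- a share b of women in each arm with the symptom before surgery who still report it afterwards, b = 10%, 20% or 30%;
- no worsening among those women;
- two-sided 5% level, 80% power, equal arms.

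**Formulas.**
- Current plan, if persisting prior symptoms are counted: q = b + (1−b)p.
- New-or-worse rule, with no worsening: r = (1−b)p.
- Number per arm: n = (1.96 + 0.84)² × [x1(1−x1) + x2(1−x2)] / (x1−x2)², where (1.96 + 0.84)² = 7.84 and x1, x2 are the two observed rates.

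**Reference, b = 0.** 7.84 × (0.24 + 0.16) / 0.04 = 78.4 per arm, risk ratio 0.50.

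**One row in full, b = 10%.**
- Current plan: 46% v 28%. n = 7.84 × (0.2484 + 0.2016) / 0.0324 = 108.9. Risk ratio 28/46 = 0.61.
- New or worse: 36% v 18%. n = 7.84 × (0.2304 + 0.1476) / 0.0324 = 91.5. Risk ratio 18/36 = 0.50.

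**All rows (n rounded up).**

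| b | Current plan | Risk ratio | n per arm | New or worse | Risk ratio | n per arm | Difference, both rules |
|---|---|---|---|---|---|---|---|
| 10% | 46% v 28% | 0.61 | 109 | 36% v 18% | 0.50 | 92 | 18 points |
| 20% | 52% v 36% | 0.69 | 147 | 32% v 16% | 0.50 | 108 | 16 points |
| 30% | 58% v 44% | 0.76 | 196 | 28% v 14% | 0.50 | 129 | 14 points |

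The absolute difference is (1−b) × 20 points under either rule. The rule restores the risk ratio and removes the background events; it does not bring back the full 20 points.

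**Sensitivity to the assumed rates, at b = 20%.**
- True rates 50% v 30%: the current plan gives 60% v 44%, risk ratio 0.73, n = 7.84 × (0.24 + 0.2464) / 0.0256 = 149.0. New or worse gives 40% v 24%, risk ratio 0.60 as in truth, n = 7.84 × (0.24 + 0.1824) / 0.0256 = 129.4.
- True rates 60% v 40%: the current plan gives 68% v 52%, risk ratio 0.76. New or worse gives 48% v 32%, risk ratio 0.67 as in truth. The variance terms coincide (0.2176 + 0.2496 = 0.4672), so n = 7.84 × 0.4672 / 0.0256 = 143.1 either way.

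The risk ratio is preserved throughout. The saving in numbers shrinks as rates rise and is nil at 60% v 40%.

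**Comparing only women free of the symptom at baseline** restores the 20 points within that group. The number to enrol is 78.4/(1−b) = 87.1, 98.0 or 112.0 per arm for true rates of 40% v 20%. Baseline status is fixed before randomisation, so this comparison keeps the protection of randomisation.

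**No true effect.** If p1 = p2, then q1 = q2. The type I error is not inflated.

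**The case against.** Several points on the other side are sound and limit the claim.

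- **Randomisation balances prior symptoms in expectation.** A reader might infer that the missing baseline favours one arm or produces false positives. It does neither. Comparing post-operative presence of symptoms between randomised arms is valid; it answers a somewhat different question from incidence, and answers it less sharply.
- **No scoring rule is written.** A reader might infer that the plan counts prior symptoms as events. It does not say so, and both the word incidence and the description of the events as post-surgical can be read as meaning new events. What stands is that no instruction tells the assessor how to apply that meaning, and no data are collected that would allow it.
- **Not every item is affected.** Participants must be mentally able to take part and must show a good understanding before consenting, so marked sedation or confusion on arrival is unlikely. Respiratory depression beforehand should be rare too. The point concerns the commoner, milder symptoms.
- **The fix has limits.** A reader might infer that a baseline check returns the requirement to 78.4 per arm. Under the new-or-worse rule it does not: women with an unchanged prior symptom stay in the denominator as non-events.
- **The size is unknown.** One value of b for an unspecified symptom is a simplification, and a prior symptom matters only if it is still reported at 6 hours or later.

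**Conclusion.** The point holds as a loss of sharpness on a secondary objective. The plan cannot separate new symptoms from persisting ones, so the rates in both arms may be too high and the risk ratio too close to 1. With assumed true rates of 40% v 20% and b from 10% to 30%, the risk ratio of 0.50 becomes 0.61 to 0.76, and about 109 to 196 women per arm are needed where the new-or-worse rule needs about 92 to 129.

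These figures rest on assumed rates, the same b in both arms and no worsening. The direction of the attenuation follows whenever b is above zero and persisting symptoms are counted; the saving in numbers also depends on the symptom rates. The documents do not support a claim that the Aim 3 comparison is biased toward either arm. Nor do they support a claim that it is underpowered by a known amount, since they give it no sample size or power target.

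The change is still worth making before enrolment, because it is cheap and the missing answer cannot be supplied later.

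**What to change.** 1. In section 3, have the existing symptom list asked once more: after consent, before randomisation and before the neuraxial injection.
2. In Specific Aim 3, define an event as a listed symptom that is new, or worse than the baseline answer. Alternatively, adjust for the baseline answer symptom by symptom. State which analysis is the main one. Judging worsening requires a simple grade (for example none, mild, moderate, severe) at baseline and at each later time.
3. Report the raw proportions with each symptom at 6, 24, 48 and 72 hours as a supporting table. This also shows any prior symptom that lasts longer in one arm without worsening, which the new-or-worse definition would miss.

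Cost: one more pass through a short list, a sentence in the aim and, if worsening is graded, a column on the form. No treatment or procedure changes. The small downside is that a woman with a prior symptom contributes an event for that symptom only if it worsens.

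### The somnolence item as collected includes tiredness and overlaps with sedation, so it is broader than the secondary endpoint it is meant to measure (minor)

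*Combined protocol and SAP*

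**What the plan says.** The endpoint is named in two places. The Summary/Program Objective lists opiate-related adverse events among the secondary objectives, "defined as somnolence, sedation, confusion, respiratory depression, dry mouth, nausea, vomiting, constipation, urinary retention and pruritus". Specific Aim 3 in section 1 expects fewer of them with the block: "The TAP block group will have a decreased incidence of opiate- related side effects such as somnolence, sedation, confusion, respiratory depression, dry mouth", and so on through the same ten effects. Somnolence and sedation are separate entries in both places, and neither place mentions tiredness.

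How the events are collected appears only in section 3, Research Design and Methods. It says "At all-time points patients and/or nurses taking care of the patient will be asked about" a list of symptoms: "somnolence (sedation or excessive tiredness), respiratory depression, hypoxia, dry mouth, nausea, vomiting, itching, constipation, urinary retention, sedation, and confusion". The list opens with somnolence, explained as either sedation or tiredness, and names sedation again near its end ("urinary retention, sedation, and confusion").

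The document gives no severity threshold, sedation scale or rule for attributing a symptom to opioids. It does not say whether incidence in Aim 3 means each symptom separately, at least one symptom, or a total.

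**The concern.** Aim 3 is about effects caused by opioids. Every participant has just had a baby by surgery, and the eligibility text in section 3 also admits women whose labor did not progress. Some will be very tired for reasons unrelated to opioids. Because the two parts of the somnolence item are joined by *or*, such a woman meets the item with no opioid effect at all.

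Events of this kind, arising in both arms, narrow the observed difference in somnolence and raise the reported rate of an effect labelled opiate-related. The same happens to any at-least-one-effect summary or total that includes the item. Once the two are recorded as one answer, the analysis cannot separate tiredness from drowsiness. The standalone sedation item recovers only part of what is lost, because drowsiness that nobody calls sedation stays mixed with tiredness.

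**Working it through.** **Inputs.** From the document: the wording of the item, its collection from patients and/or nurses, and four time points (6, 24, 48 and 72 hours). Not in the document: any rate of tiredness, somnolence or sedation, a sample size, or an analysis of Aim 3. There is no figure of the plan's own to reproduce, and every rate below is an assumption.

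**Step 1: the two lists.** The Summary and Aim 3 name ten effects. The section 3 list has eleven entries, because it adds hypoxia. The difference that matters here is the tiredness wording inside somnolence. None of the other entries carries it.

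**Step 2: dilution.** Let s be the true rate of opioid-related somnolence in an arm and b the background rate of tiredness, equal in both arms and independent of s.

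- Recorded rate: r = 1 - (1 - b)(1 - s).
- Recorded difference: r1 - r2 = (1 - b)(s1 - s2).
- Information needed relative to b = 0: [r1(1 - r1) + r2(1 - r2)] / (r1 - r2)², divided by the same quantity at b = 0. For s = 20% vs 10%, that quantity at b = 0 is (0.16 + 0.09)/0.10² = 25.

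| b | Recorded rates | Difference (points) | Relative information |
|---|---|---|---|
| 0 | 20% vs 10% | 10 | 1.0 |
| 10% | 28% vs 19% | 9 | 0.3555/0.09² = 43.9; 43.9/25 = 1.8 |
| 20% | 36% vs 28% | 8 | 0.4320/0.08² = 67.5; 67.5/25 = 2.7 |
| 40% | 52% vs 46% | 6 | 0.4980/0.06² = 138.3; 138.3/25 = 5.5 |
| 60% | 68% vs 64% | 4 | 0.4480/0.04² = 280; 280/25 = 11.2 |

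With higher assumed rates, 40% vs 20%, the number per arm for 80% power at two-sided 5% is 82 at b = 0, 150 at b = 0.2 and 356 at b = 0.5. The pattern is the same.

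**Step 3: repeated questions.** If incidence means ever reported over the four time points, an assumed 20% background per visit gives a b between 20% (the same women each time) and 1 - 0.8⁴ = 59% (independent visits). The document does not say that incidence is counted this way.

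**Step 4: reach.** For an at-least-one-effect summary, the same formula applies, with s as the rate of any effect without tiredness. In symptom-by-symptom comparisons b enters only the somnolence row.

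**Step 5: the repeated sedation item.** In an at-least-one-effect summary the overlap adds nothing, because the union counts a woman once. In a symptom-by-symptom analysis it gives two overlapping rows. Only a summed count of items would count sedation twice.

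**The case against.** The strongest reply is that the repetition protects the endpoint. Sedation is asked about at every time point as its own item, without the tiredness wording, so opioid sedation is still recorded cleanly. This stands. A reader might infer that the wording would hide a real reduction in opioid sedation, or that Aim 3 as a whole is diluted. Neither follows: one of the ten named effects is affected, plus any summary that includes it.

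A reader might also infer that sedation is counted twice. The document has no counting rule, so all that can be said is that it is collected under two items.

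Nor does the text support the inference that most participants would be recorded with an event. No rate of tiredness is given, and the wording requires the tiredness to be excessive.

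The parenthesis may be a lay explanation and not a case definition, since the nearby text addresses the patient directly. That is possible. But it is the only statement of what will be asked, and answers will follow it.

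Finally, tiredness may partly be an opioid effect. If so, the broader item captures some real signal, and the factor (1 - b) overstates the loss. This also stands, and it is a reason to keep tiredness as a separate record instead of discarding it.

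**Conclusion.** The point holds in a limited form. The somnolence item is broader than the endpoint named in the Summary and Aim 3, and it overlaps with sedation. A background of tiredness in both arms would move that item, and any composite or total containing it, towards no difference.

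The direction rests on a modest assumption: some tiredness in both arms that is not caused by opioids. The size cannot be stated. For an assumed 20% vs 10%, the information needed rises 1.8 to 2.7 times at b = 10% to 20% and 11.2 times at b = 60%, given equal and independent background. The large figure should not be read as an estimate for this trial.

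The endpoint is secondary, and a background equal in both arms works against the trial's hypothesis, so it would not create a false benefit. This is a minor issue, worth correcting because the correction is easy and the answers cannot be separated afterwards.

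**What to change.** - In the section 3 question list, take tiredness out of somnolence and record it as its own item, outside the opiate-related count.
- Merge somnolence and sedation into a single drowsiness/sedation item, and make the same change in the Summary/Program Objective and Specific Aim 3, so that the three places agree and the item enters any count once. This needs no severity threshold. One set at marked sedation would lose milder drowsiness.
- State that Aim 3 is compared symptom by symptom, and whether incidence means ever reported or reported at each time point.

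The cost is a line on the question form and matching edits in two other places, with no added visits or staff. The downside is that opioid fatigue without drowsiness no longer counts as opiate-related, though it is still recorded and can be reported separately by arm.
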